## 7.0 Data and Specimen Banking\*

7.1 All information will be retained for five years after the completion of the study. Only the PI, research staff and data managers will have access to this information.

All paper documents will be securely stored in the participant's research file, which will be kept in a locked cabinet in research team offices within secure buildings. In all data sets, including those with genetic testing and counseling information, we will use ID numbers only. A separate data set linking names with ID numbers will be accessible only through password protected and secure data programs and available only to trained study staff.

**7.2** What data will be stored:

- Hospital/physician medical records
- Lab, pathology and/or radiology results
- Interviews/questionnaires

**7.3** This data will not be shared.

**8.0** **Sharing of Results with Subjects\***

*8.1* Upon receipt of a positive genetic test result or a variant of uncertain clinical significance, participants in either arm will be contacted by a board-certified genetic counselor to schedule a telephone disclosure session. This session will follow standard clinical protocols for the delivery of genetic test results. Participants in the ST arm who receive a negative result will be notified by mail only, but may choose to schedule a free telephone genetic counseling session if they wish. They and their referring physician will receive a copy of the test report along with a standard clinical letter prepared by a board-certified genetic counselor.

**9.0** **Study Timelines\***

*9.1* Participants will remain in the study for 3 months after randomization.

We expect participant enrollment to be completed within three-months.

The anticipated study completion date is 9/1/20.

**10.0** **Inclusion and Exclusion Criteria\***

*10.1* Screening for Eligibility: The Survey, Recruitment and Biospecimen Collection Shared Resource (SRBSR) will work with our clinical collaborators to obtain a list of potentially eligible patients from the clinical databases and the EMR. To each potentially eligible patient, we will mail an introductory letter (from the study Principal Investigators and the patient's physician), opt-out postcard/phone number, informed consent document and baseline survey (we will also email electronic versions of these materials). Two-weeks following this mailing, we will call all patients who have not opted out or completed the baseline survey. At the start of this telephone call we will confirm study eligibility.

*10.2* Inclusion Criteria:

- Men who are being followed at MGUH or MWHC for metastatic prostate cancer or Gleason 7+ prostate cancer.

Exclusion Criteria:

- Above age 80.
- Previous cancer genetic counseling or currently scheduled for cancer genetic counseling related to the *BRCA1* or *BRCA2* genes.
- Have had or are scheduled for germline cancer genetic testing of the *BRCA1* or *BRCA2* genes.
- Cannot participate in English
- Are not capable of providing informed consent

*10.3* We will exclude adults unable to provide meaningful informed consent, individuals under the age of 18 and prisoners. Since the study focuses on prostate cancer survivors, women are ineligible.

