## 1.0 Study Summary

Study Title	Streamlined Genetic Testing In Prostate Cancer
Study Design	Pilot Randomized Controlled Trial
Primary Objective	To evaluate the impact and efficacy of a streamlined genetic education and testing intervention for men with prostate cancer.
Secondary Objective(s)	
Research Intervention(s)/ Investigational Agent(s)	Streamlined genetic education and testing intervention.
IND/IDE #	n/a
Study Population	Eligible participants are men who are currently being followed at MGUH or MWHC for metastatic prostate cancer or Gleason 7+ prostate cancer with Ashkenazi Jewish ancestry or Gleason 7+ with a family history of breast, ovarian, pancreatic or prostate cancer.
Sample Size	120
Study Duration for individual participants	Three-months.
Study Specific Abbreviations/ Definitions	MGUH: Medstar Georgetown University Hospital; MWHC: Medstar Washington Hospital Center; PV: Pathogenic Variant; VUS: Variant of Uncertain Significance; ST: Streamlined Testing; UC: Usual Care; EMR: Electronic Medical Record; SRBSR: Subject Recruitment and Biospecimen Shared Resource

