## 2.0 Objectives\*

Genetic testing is established as part of clinical care for women with breast and ovarian cancer. Clear guidelines have led to increasing genetic testing participation among eligible women. Identifying pathogenic variants (PVs) in cancer susceptibility genes has important treatment, management and risk reduction implications for breast and ovarian cancer patients and their family members. Men are just as likely as women to carry a PV in a cancer risk gene and men with prostate cancer are at particularly high risk for carrying a PV. NCCN guidelines recommend germline genetic testing in all men with metastatic prostate cancer or with Gleason 7+ prostate cancer and Ashkenazi Jewish ancestry or a family history of prostate, breast, ovarian or pancreatic cancer. These guidelines are likely to expand given recent studies suggesting that 17% of prostate cancer patients may harbor a cancer susceptibility PV and that current referral criteria miss many of these patients. Prostate cancer patients with a PV in *BRCA1* or *BRCA2* (*BRCA*) have more aggressive prostate cancers, are at risk for other primary cancers (e.g., male breast and pancreatic) and their family members are at risk for a variety of cancers. Thus, genetic testing of prostate cancer patients has implications for treatment, management, and risk reduction for the patient and his family members.

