## **6.0 Procedures Involved\***

6.1-6.4 The objective is to develop and pilot a novel streamlined approach to deliver genetic education and testing to the rapidly increasing number of prostate cancer patients who meet guidelines for genetic referral. Our streamlined genetic testing approach is designed to facilitate genetic education and testing for men with prostate cancer. The intervention will incorporate proactively delivered print educational materials in lieu of pre-test genetic counseling. The materials will increase awareness, expand access, provide

balanced information to foster informed genetic testing decisions and reduce barriers to facilitate the delivery of genetic testing. All men who are found to carry a PV or variant of uncertain significance (VUS) in a cancer risk gene will have an individual telephone genetic counseling disclosure session with a board-certified genetic counselor. We will recruit 120 prostate cancer survivors who meet clinical referral criteria. After a baseline survey, we will randomize participants to: ST vs. UC. Participants will complete a follow-up survey at 2-3-months post-randomization. Our primary outcome is genetic testing uptake.

Eligibility and Accrual. Men eligible for this study are currently being followed at MGUH or MWHC for either:

Metastatic prostate cancer;  
Gleason 7+ prostate cancer.

We will exclude patients who have had, or are already scheduled for genetic counseling or testing for *BRCA1* or *BRCA2* mutations. We will also exclude men who cannot participate in English and provide meaningful consent. We will recruit participants from medical and radiation oncology clinics at MGUH and MWHC. These clinics currently follow well over 1000 eligible patients.

Gender and Minorities. Participants will be adult men. Given the racial/ethnic breakdown of the clinics we are recruiting from. We expect that at least 30% of participants will be members of racial/ethnic minority groups.

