There may also be risks for ST participants who proceed directly to genetic testing without an individual genetic counseling session. However, we believe that the risk to these participants is low for several reasons. A) In community practice approximately 50% of individuals who receive cancer genetic testing do so without any pre-test genetic education or counseling; B) All participants who are randomized to ST will have the option to request individual telephone genetic counseling free of charge through the study; C) All individuals who proceed to genetic testing and are found to carry a PV or VUS result will receive their test results in the context of a standard genetic counseling disclosure session with a board-certified genetic counselor; D) The population in the current study all meet guidelines for genetic referral. There are insufficient counseling resources to retrospectively contact and counsel all prostate cancer survivors who meet criteria for genetic testing. Thus, from a clinical perspective, it is critical to develop effective and efficient genetic education approaches to foster informed genetic testing decisions. Finally, the personal health implications of a positive genetic test result in men are much less pronounced and immediate than in women. Thus, the risk of adverse psychosocial outcomes (already low in women who undergo testing) is quite low.

For all patients who choose to proceed with genetic testing, there may be additional risks. Although participants will neither be encouraged nor discouraged from undergoing testing as part of this study, for those who choose to pursue testing, additional potential risks include insurance and employment discrimination and the small possibility of incorrect or inaccurate test results. The ST materials contain information about laws protecting against genetic discrimination, and the standard clinical laboratory consent form outlines the small possibility of incorrect or inaccurate test results.

Finally, in addition to psychosocial risks that may be associated with genetic counseling, there may also be risks related to confidentiality and loss of privacy should an unauthorized third-party learn that the participant received genetic counseling and testing.

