## 24.0 Setting

24.1 All study participants will be patients of our collaborating medical and radiation oncologists at MGUH and MWHC. Participants who are potentially eligible for the study (i.e., meet clinical genetic referral criteria) will be identified via EMR query and then contacted by the study team. All research procedures will be conducted remotely (survey completion, delivery of print genetic education and telephone genetic counseling).

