## 25.0 Resources Available

25.1 *Recruiting Feasibility:* Men eligible for this study are currently being followed at MGUH or MWHC for metastatic prostate cancer or Gleason 7+ prostate cancer with a family history of breast, ovarian, pancreatic or prostate cancer or Ashkenazi Jewish ancestry. We will exclude patients who have had or are scheduled for, genetic counseling or testing. We will also exclude men who cannot participate in English and provide meaningful consent. We will recruit participants from medical and radiation oncology clinics at MGUH and MWHC (see letters of

support in attached protocol). These clinics currently follow well over 1000 eligible patients. Although we routinely attain 70% case participation, we can attain our required sample size (n=120) with much lower rates of participation.

*Time:* The project will be conducted over the next year with data analysis and manuscript preparation continuing for 1 years after the completion of participant follow-up.

*Facilities:* Participants will be contacted via mail, telephone and electronically. The study staff will initiate these contacts from the Cancer Prevention and Control office suite and from the offices of SRBSR in MGUH. Each member of the study staff has a private or semi-private office with private telephone and private secured workstations. Each office is locked and accessible only by the study staff member and the PI or Project Director. All DNA will be collected using standard DNA saliva kits used by the study participants in the privacy of their home. DNA will be shipped by mail to the designated commercial genetic testing company for preparation and sequencing in a secure and CLIA-approved facility as is standard for all clinical genetic testing samples.

*Medical and Psychological Resources:* This is a low-risk study. However, all participants will have access to a board-certified genetic counselor. All of these counselors are trained and experienced at recognizing signs of psychological distress. All positive genetic test results will be delivered by a board-certified genetic counselor who will assess psychological reactions to genetic test results and make referrals for additional services as needed. All negative or VUS results will be delivered via mailed clinical letter and will include contact information for the assigned genetic counselor in case the participant wishes to schedule a session.

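### Sections 6.0 and 10.2 admit any man with Gleason 7+ disease, Sections 1.0 and 25.1 only those with a family history or Ashkenazi Jewish ancestry, and statements about all participants fit only the narrower rule

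*Combined protocol and SAP*

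**What the plan says.** The eligibility rule for Gleason 7+ disease appears in two forms.

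- **Broad.** Section 10.2 gives the inclusion criterion as "Men who are being followed at MGUH or MWHC for metastatic prostate cancer or Gleason 7+ prostate cancer". Section 6.0 (Eligibility and Accrual) opens with "Men eligible for this study are currently being followed at MGUH or MWHC for either" and then lists metastatic disease and Gleason 7+ disease without further condition.
- **Restricted.** The Study Population entry in Section 1.0 takes Gleason 7+ men with Ashkenazi Jewish ancestry, or "Gleason 7+ with a family history of breast, ovarian, pancreatic or prostate cancer". Section 25.1 repeats the restriction: "metastatic prostate cancer or Gleason 7+ prostate cancer with a family history of breast, ovarian, pancreatic or prostate cancer or Ashkenazi Jewish ancestry".

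Section 2.0 describes the testing guideline, beyond metastatic disease, as covering "Gleason 7+ prostate cancer and Ashkenazi Jewish ancestry or a family history of prostate, breast, ovarian or pancreatic cancer". Section 3.0 describes it with the same qualifier for localised disease.

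Several statements then apply to every participant:

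- Section 6.0, opening paragraph: "We will recruit 120 prostate cancer survivors who meet clinical referral criteria".
- Section 15.1, point D of the reasons why proceeding without counselling is low risk: "The population in the current study all meet guidelines for genetic referral".
- Section 24.1: "Participants who are potentially eligible for the study (i.e., meet clinical genetic referral criteria) will be identified via EMR query".
- Sections 2.0, 5.0 and 6.0: each usual-care (UC) man is informed, by letter in 5.0 and 6.0, that he meets the guidelines or eligibility criteria for genetic counselling or testing.

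**The concern.** The inclusion criterion decides who is enrolled, and here the body of the protocol gives two different answers. If staff confirm eligibility against Section 10.2 as written, they will enrol men outside the population defined in Sections 1.0 and 25.1.

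Three things are then at stake. First, the UC letter would tell some men something that the protocol's own description of the guideline does not support. Second, one of the four stated grounds for regarding the streamlined (ST) route as low risk would not hold for them. Third, a reader could not tell which population the pilot's uptake rates and effect sizes describe, although these are meant to inform a larger trial.

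**Working it through.** **Step 1. Set the criteria side by side.**

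| Place | Metastatic | Gleason 7+ with ancestry or family history | Gleason 7+, non-metastatic, neither qualifier |
|---|---|---|---|
| 1.0 Study Summary | in | in | out |
| 25.1 Recruiting Feasibility | in | in | out |
| 6.0 Eligibility and Accrual | in | in | **in** |
| 10.2 Inclusion Criteria | in | in | **in** |
| Guideline as described in 2.0 and 3.0 | covered | covered | not covered |

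Only the last column differs.

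**Step 2. Look for something that removes these men.** The exclusions in 10.2 concern age above 80, earlier or scheduled BRCA counselling or testing, English, and capacity to consent. Section 10.3 adds minors, prisoners and women. None touches family history or ancestry.

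**Step 3. Test the universal statements on a man in the last column.** Read with Section 2.0, he does not meet the guideline. The referral-criteria sentence in 6.0, the definition in 24.1, point D in 15.1 and the UC letter are therefore each untrue of him. Section 2.0 says the guidelines are likely to expand, not that they had.

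**Step 4. Check the recruitment pool.** Sections 6.0 and 25.1 give the same figure, well above 1,000 eligible patients, one under the broad rule and the other under the restricted rule. The documents do not say which definition was counted.

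**Step 5. See whether the sample size is affected.** The inputs come from Section 17.1 (Power) and Table 2: two-sided alpha 0.05, 80% power, UC uptake p1 = 0.20, ST uptake p2 = 0.45, 120 men in total. Allocation is 1:1 (Section 6.0), hence 60 per arm. The formula is the pooled normal approximation:

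n = [1.960·√(2·p̄·(1−p̄)) + 0.842·√(p1(1−p1) + p2(1−p2))]² / (p2−p1)², with p̄ = 0.325

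= [1.960·√0.43875 + 0.842·√0.4075]² / 0.0625 = (1.298 + 0.537)² / 0.0625 = 53.9, so **54 per group**, as in Table 2.

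Power with 60 per arm = Φ[(0.25·√60 − 1.298) / 0.638] = Φ(1.00) = **84%**.

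If a share f of the sample lies in the last column, ST uptake becomes 0.45(1−f) + f·s, where s is ST uptake in those men. The documents give neither f nor s. The table assumes values for both and holds UC uptake at 20%:

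| Assumed f | s = 20% (no effect) | s = 35% | s = 45% | s = 55% |
|---|---|---|---|---|
| 25% | 62% | 76% | 84% | 90% |
| 50% | 34% | 67% | 84% | 94% |

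For example, f = 25% and s = 35% gives 0.75·0.45 + 0.25·0.35 = 0.425, and 20% versus 42.5% with 60 per arm has 76% power. Letting UC uptake in these men also vary, from 10% to 30%, with f = 25% and s between 35% and 55%, widens the range to 65% to 95%. Power could move either way, so the table shows sensitivity and does not estimate harm.

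**The case against.** The strongest reply has four parts.

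1. *The rules are nested.* Everyone who meets the restricted rule also meets the broad one, so enrolling only qualified men would breach neither. That is correct, but it does not tell staff what to do with a man in the gap. Section 10.2 makes him eligible.
2. *The restriction is applied upstream.* Section 24.1 places referral criteria at the EMR query, and the opening of Section 6.0 can be read as a further condition on the list below it. This suggests that the narrower rule may be intended. However, eligibility is confirmed later by screener or telephone call, and the written list to check against is 10.2, which passes these men. Sections 6.0 and 10.2 also agree with each other, so the text does not settle the intent.
3. *The untruth of the statements is an inference.* Sections 2.0 and 3.0 do not use the word only, the UC letter itself is not in the documents, and its paraphrases differ between counselling and testing. This stands as a limit: the conclusion depends on reading referral criteria as the guideline the protocol describes. The documents offer no other definition.
4. *The practical harm is small.* The study is described as minimal risk, counselling is free in both arms, and the planned larger trial concerns newly diagnosed men, so its effect sizes must cross populations anyway. This limits the consequences but does not remove the conflict in the rule for entry.

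**Conclusion.** The concern holds. The operative inclusion criterion conflicts with the population stated in Sections 1.0 and 25.1, and following it as written would make statements to and about some participants untrue by the protocol's own account. It should be corrected because it governs enrolment and the accuracy of a participant letter, not because of any loss of power.

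The number of men affected cannot be derived from the documents. Only non-metastatic Gleason 7+ men with neither qualifier are involved. The between-arm comparison remains valid, and no stated sample-size figure changes. The conclusion rests on one assumption: that the guidelines and referral criteria mentioned throughout are those described in Sections 2.0 and 3.0.

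**What to change.** Use one identical eligibility criterion in Sections 1.0, 6.0, 10.2 and 25.1, and align 15.1 and 24.1 with it. The sponsor must state which version is intended.

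- **If restricted:** add the ancestry or family-history condition after Gleason 7+ in 6.0 and 10.2.
- **If broad:** remove the condition from 1.0 and 25.1. Correct the referral-criteria sentence in 6.0, point D in 15.1, the definition in 24.1 and the description of the UC letter in 2.0, 5.0 and 6.0. Also report by arm how many men met the guideline. Family history is already collected at baseline (Table 1), but ancestry is not listed there by name and would have to be recorded.

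In either case, say which definition the pool of more than 1,000 patients refers to. As a minor related point, Section 2.0 limits enrolment to men diagnosed between 2010 and 2019, and 10.2 should state whether that window applies.

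The cost is amendment wording. The restricted version may reduce the recruitment pool by an unknown amount. The broad version needs revised letters and one extra baseline item.

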## **11.0 Vulnerable Populations\***

*11.1* This research does not involve individuals from vulnerable populations.

## **12.0 Local Number of Subjects**

*12.1* 120 subjects will be recruited locally.

## **13.0 Recruitment Methods**

*13.1* Working with our clinical collaborators, the Survey, Recruitment and Biospecimen Collection Shared Resource (SRBSR) will obtain contact information of potentially eligible patients from the clinical databases and the EMR. We will mail an introductory letter (from the study MPIs and the patient's physician), opt-out postcard/phone number, informed consent document and baseline survey (we will also email electronic versions of these materials) to all potentially eligible patients. Participants who do not wish to be contacted further for the study or are ineligible for the study will be able to easily opt out using an enclosed postcard, toll-free telephone line or electronic mail address. Patients who have questions about the study can also contact the study team via the toll-free telephone line.

Two-weeks following the initial study mailing, we will call patients who have not completed the baseline survey or opted out. After confirming eligibility, explaining the study and answering any questions, an SRBSR RA will administer an IRB-approved verbal consent for the baseline survey. A verbal consent will allow us to complete the minimal risk baseline survey in a timely fashion. Participants will then be required to complete the print or electronic informed consent document prior to randomization. We have successfully used this approach in multiple previous trials. After providing informed consent, participants will complete the 10-minute baseline survey over the telephone (participants will have the option to complete the survey electronically).

*13.2* Subject Source: Participants will be prostate cancer patients/survivors who are currently being followed by one of our physician co-investigators (i.e., have had an appointment in July 2017 or later).

*13.3* Method to identify subjects: Prostate cancer patients who are currently being followed by one of our physician co-investigators will be identified via clinical databases or through the EMR. We will generate a list of patients who potentially meet our eligibility criteria. Each of these patients will be mailed a packet of study information and will have eligibility confirmed via an eligibility screener or contact by the SRBSR.

*13.4* Participants will be identified by their treating physician who will query the clinical records for patients who meet the study eligibility criteria.

*13.5* Recruitment Materials: Study staff will mail a packet to potentially eligible patients. This mailing will include: an introductory letter describing the study, information about how to opt out of the study or to speak to a study team member with any questions, an informed consent document and a print version of the baseline survey. For patients with email addresses available, we will also send these materials electronically.

*13.6* Participants will receive an incentive of \$20 upon completion of the baseline survey and another \$20 incentive upon completion of the follow-up survey.

